1.0 Study Synopsis

Objectives:

Primary:

1. To evaluate the safety of primary and boost vaccinations with lethally irradiated allogeneic pancreatic tumor cells transfected with the GM-CSF gene vaccine in the treatment of patients with surgically resected adenocarcinoma of the head, neck, or uncinate of the pancreas

Secondary:

1. To estimate the association of specific *in vivo* parameters of immune response including, but not limited to mesothelin, prostate stem cell antigen (PSCA), and mutated *k-ras*-specific T cell responses, with clinical responses in patients who are receiving semi-annual vaccine boosting with lethally irradiated allogeneic pancreatic tumor cells transfected with the GM-CSF gene.
2. To estimate the efficacy of vaccine boosts in the treatment of patients with adenocarcinoma of the pancreas in terms of overall and recurrence free survival.
3. To use the serum GM-CSF levels as a measure of longevity of an allogeneic vaccine following a semi-annual boosting with lethally irradiated allogeneic pancreatic tumor cells transfected with the GM-CSF gene.
4. To determine the psychosocial and symptom profiles of patients with pancreatic cancer treated with an irradiated allogeneic GM-CSF secreting vaccine, and to explore changes over time. The psychosocial profile will include information about, but is not limited to demographics, quality of life, hope, trust, social support, decision control and advanced directives. The symptom profile will include but is not limited to pain, anorexia, fatigue, and mood state.

Study population:

In order to be considered for this study, patients need to meet following major criteria for inclusion: History of surgically resected pathologic stage 1 (no direct tumor extension beyond pancreas and no regional lymph node metastases), 2 (direct extension of tumor beyond pancreas), and/or 3 (regional lymph node metastases) adenocarcinoma of the head, neck, tail, or uncinate of the pancreas.

Have no radiographic evidence of pancreatic cancer disease recurrence.

Have not received any anti-cancer therapy in the past 28 days.

Study Design:

Eligible subjects will receive by intradermal administration the pancreatic tumor vaccine consisting of two irradiated, allogeneic pancreatic tumor cell lines transfected with the granulocyte macrophage-colony stimulating factor (GM-CSF) gene. There will be two cohorts of research participants: those who have previously received the pancreatic cancer vaccine (up to 17) and those

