The sample size was expanded to include a cohort of up to 45 vaccine-naïve research participants and 17 previously vaccinated research participants for a total sample up to 62 research participants.

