4.3 Analysis of Secondary Endpoints

The analysis of the remaining endpoints are primarily descriptive in nature and are intended to be used to generate estimates of efficacy and hypotheses to be tested in later trials. For each endpoint, separate analyses will be performed for the vaccine naïve and vaccine treated patients.

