Measurements of immune response include but are not limited to mesothelin, prostate stem cell antigen (PSCA) and mutated k-ras-specific T cell responses. Continuous variables will be summarized with means and standard deviations. Dichotomous and categorical variables will be

summarized using proportions with exact 95% confidence intervals and counts, respectively. These summaries will be computed for each patient at two time points around each vaccine boost: pre-vaccination and four weeks post vaccination. Plot will be used to show the changes in immune response over time both for each individual and for each cohort. For each vaccine boost, comparisons in the pre and post-vaccine responses will be compared using paired t-tests (or Wilcoxon signed rank tests if appropriate) for continuous variables and Fisher's exact test for dichotomous or categorical variables. Associations between immune responses will be explored graphically (e.g. scatterplots, boxplots) and numerically (e.g. correlations, χ^2 tests).

Measurements of antitumor immunity include but are not limited to the measurement of shared tumor-specific antigens and k-ras specific antitumor immune responses. Autologous lymphocytes will be obtained from peripheral blood before each vaccination, and at four weeks following each vaccinations. The graphical and numerical analyses of these results will be the same as that described for measurements of immune responses and will be carried out for each cohort separately.

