4.3.4 Psychosocial and symptom profiles

The psychosocial and symptom profiles will be evaluated through the use of a variety of surveys and measurement tools. Surveys will be administered at several time points: day 0 and day 28 of the each vaccination. The responses will be measured using 8 techniques described in Section 5.3 and include topics such as concept of hope, symptom burden, patient satisfaction, and QOL. Categorical measurements such as those based upon Likert scales (e.g. Hearth Hope Index) will be summarized using counts, medians, ranges and estimates of the probability distributions. Continuous variables will be summarized using means and standard deviations. Trends over time

will be summarized by plotting the median measurements against time with an estimate of variability (e.g. standard deviation, inter-quartile range) for each cohort. Associations between measurements will be evaluated graphically (e.g. boxplots, scatterplots) and numerically (e.g. Spearman's correlation). Comparisons between time points will be made using non-parametric techniques (e.g. Kruskal-Wallis test, χ^2 test).

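### The tests named for comparing survey scores between time points assume independent groups, although the same patients answer each time, so the comparison is conservative and loses power

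*Combined protocol and SAP*

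**What the plan says.** Section 4.3.4 sets the timing: "Surveys will be administered at several time points: day 0 and day 28 of the each vaccination". Section 5.3 repeats days 0 and 28. The method for comparing time points is one sentence: "Comparisons between time points will be made using non-parametric techniques", with the Kruskal-Wallis and chi-square tests as its only examples. The only other treatment of change over time is graphical. Trends "will be summarized by plotting the median measurements against time with an estimate of variability", by cohort.

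Secondary objective 4 in the Study Synopsis is to determine the psychosocial and symptom profiles "and to explore changes over time". Section 4.3 adds that "separate analyses will be performed for the vaccine naïve and vaccine treated patients". Section 4.1 caps the cohorts at "a cohort of up to 45 vaccine-naïve research participants and 17 previously vaccinated research participants".

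For pre- and post-vaccination immune responses, section 4.3.1 does use pairing. These are "compared using paired t-tests (or Wilcoxon signed rank tests if appropriate) for continuous variables".

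**The concern.** Kruskal-Wallis and the chi-square test treat the scores at each time point as coming from different people. Here they come from the same people. Stable differences between patients then stay in the error term, although pairing would remove them. The tests become too cautious, and a null result could be read as evidence of no change when the method had little chance of showing one.

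This sentence is the only inferential method given for the change-over-time part of objective 4. A correction to section 4.3.1 would not reach it. Because the cohorts are analysed separately, the group of at most 17 patients gets no help from the larger one.

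Membership also changes. Section 3.4.6 takes patients off study at radiographic recurrence, so later time points hold fewer patients, selected for being recurrence-free. An independent-groups comparison mixes that selection with change within patients.

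**Working it through.** **Inputs from the documents.** Cohort maxima of 17 and 45 patients, and a full naïve cohort of 40 in the original calculation (section 4.1); separate analyses by cohort (section 4.3); Herth Hope Index scored 12 to 48 (section 5.3). The visit lists in section 3.4.1 give vaccine-naïve patients four survey occasions around priming: baseline, prime 2, prime 3, and day 28 after prime 3.

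**Assumptions, not in the documents.** Two-sided 5% level, true change of 0.5 SD, within-patient correlation ρ from 0 to 0.7, complete data. The plan states no power or error rate for this comparison, so there is no figure of its own to reproduce.

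**Step 1: why the test is conservative.** For two time points, the difference in means has variance 2(1−ρ)/n in SD units. An independent-groups test uses 2/n. With no true change, its rejection rate is approximately 2Φ(−1.96/√(1−ρ)):
- ρ = 0.3: 2Φ(−2.34) = 1.9%
- ρ = 0.5: 2Φ(−2.77) = 0.6%
- ρ = 0.7: 2Φ(−3.58) = 0.03%

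**Step 2: power by normal formula.** Independent case: Φ(0.5/√(2/n) − 1.96). Paired case: Φ(0.5/√(2(1−ρ)/n) − 1.96).
- n = 17: independent Φ(1.458 − 1.96) = 31%; paired at ρ = 0.5, Φ(2.062 − 1.96) = 54%
- n = 45: independent Φ(2.372 − 1.96) = 66%; paired at ρ = 0.5, Φ(3.354 − 1.96) = 92%

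The independent figures take ρ = 0. When the scores are correlated, the independent-groups test has power of about Φ((0.5/√(2/n) − 1.96)/√(1−ρ)). At n = 17 the bracket is negative (−0.502), so its power falls as ρ rises: Φ(−0.502/0.548) = 18% at ρ = 0.7.

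**Step 3: simulation of the rank tests.** Correlated normal scores were rounded to a 12-48 scale, with 2,000 runs per setting. The simulation standard error is at most √(0.25/2000) = 1.1 points. Two time points, Kruskal-Wallis against signed-rank:

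| n | ρ | Power, 0.5 SD change | Kruskal-Wallis rejection, no change |
|---|---|---|---|
| 17 | 0 | 29% v 26% | 5.1% |
| 17 | 0.3 | 24% v 34% | 2.7% |
| 17 | 0.5 | 22% v 47% | 0.7% |
| 17 | 0.7 | 18% v 68% | 0.2% |
| 40 | 0 | 58% v 57% | 5.2% |
| 40 | 0.3 | 60% v 73% | 2.2% |
| 40 | 0.5 | 61% v 86% | 0.7% |
| 40 | 0.7 | 63% v 97% | 0.1% |
| 45 | 0.3 | 63% v 76% | 2.3% |
| 45 | 0.5 | 68% v 89% | 0.5% |
| 45 | 0.7 | 73% v 98% | 0.1% |

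The signed-rank test stayed near 5% under no change (4.4% to 5.6%).

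Four time points, linear change reaching 0.5 SD, Kruskal-Wallis against Friedman, at ρ = 0.3, 0.5 and 0.7:
- n = 17: 11% v 21%, 9% v 33%, 4% v 51%
- n = 45: 44% v 58%, 41% v 72%, 34% v 94%

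For n = 40, a separate run gave about 28-37% v 50-90% over the same correlations.

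Binary item moving from 30% to 50%, chi-square against McNemar, correlation 0.7 on the underlying scale: 17% v 35% at n = 17 and 49% v 73% at n = 45.

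Repeat runs move these figures by a point or two, which is why the summary ranges differ slightly from the table.

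**The case against.** **The tests are only examples.** The sentence commits to non-parametric techniques, and a signed-rank or Friedman test would fit that wording. This stands: a reader might infer that the plan binds the analyst to the wrong tests, and it does not. But both examples are wrong for the design, no paired method is named for the surveys anywhere, and an analyst following the text would use what it names.

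**The analysis is descriptive.** Section 4.3 calls the secondary analyses primarily descriptive and hypothesis-generating. Section 4.3.4 sets no significance level or decision rule, and the plots of medians do not depend on the test. The error is conservative, so it creates no false claim of change. All of this stands and limits the weight of the point.

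**The loss depends on assumed values.** At ρ = 0.3 the two-time-point loss is roughly 10 to 13 points, and at ρ = 0 there is none. The four-time-point figures assume complete data. Friedman needs complete rows, so dropout would shrink its advantage: if only half of 40 patients reached the fourth survey, ρ = 0.7 gave 18% v 58% and ρ = 0.5 gave 22% v 35%. This stands as a limit on size, not on direction.

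**Repeat surveys are less clearly scheduled at boosts.** The itemised boost lists in section 3.4.1.4 contain no survey item, although the surrounding text there and sections 4.3.4 and 5.3 refer to surveys around boosts. The repeat surveys of the previously vaccinated cohort, where the two-time-point loss bites hardest, therefore rest on that general wording.

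**Conclusion.** The examples named in section 4.3.4 do not suit repeated scores from the same patients and should be changed. The consequence is reduced power in a secondary, descriptive analysis. The primary safety endpoint, the toxicity stopping rule and the sample size are untouched.

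A reader might go further and infer that real changes will probably be missed throughout. The figures do not support that. With 40 to 45 patients and two time points, Kruskal-Wallis still finds a 0.5 SD change in about 60-73% of trials. A probable miss applies to the 17-patient cohort at that change and to comparisons over four time points. Nor is the true error rate always 1% or less: at ρ = 0.3 it is about 2-3%. These sizes rest on the assumed change, correlation and complete data; the direction needs only positive within-patient correlation.

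**What to change.** Replace the examples in the last sentence of section 4.3.4, by cohort:
- two time points, scores: Wilcoxon signed-rank
- two time points, categorical items: McNemar, or Stuart-Maxwell where numbers allow
- several time points: Friedman, or a repeated-measures mixed model with a patient random effect and time as a fixed effect

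The mixed model keeps patients who miss a survey. It does not remove bias if dropout at recurrence is informative, so report the number contributing at each time point beside every comparison. Ordinal mixed models and Stuart-Maxwell may be unstable with 17 patients or fewer; the simpler paired tests are enough there.

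The cost is a short change to the analysis text. No new data or visits are needed.

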5.0 Response Criteria

5.1 Evaluation of Clinical Activity

Most patients will have only minimal residual disease at the time of enrollment. Therefore, there will be no evaluable disease to measure at baseline. Patients will be monitored for disease-free and overall survival. The results from this trial will be compared to historical controls seen at the Johns Hopkins Hospital (5). Patients recently seen at the Johns Hopkins Hospital who can be matched for pathologic stage, surgical intervention, and adjuvant combination chemotherapy and radiation therapy, are the most accurate group of historical controls since our institution has the largest reported experience treating patients with this disease and has recently reported the best survival statistics for current interventions (5).

Patients may undergo standard of care evaluations consisting of abdominal, chest, and pelvis CT scans at regular intervals to evaluate for local recurrence and distant metastases. In addition, any patient presenting with symptoms will undergo evaluation for metastases. Recurrent disease is defined as evidence of either local or metastatic recurrence by CT scan.

The serum tumor marker CA19-9 lacks a sufficient sensitivity and specificity to serve as reliable indicators of response. The CA 19-9 levels will be followed to evaluate whether large and persistent changes might correlate with either in vitro immune responses or with time to clinical recurrence.

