2. Received the last lethally irradiated GM-CSF transfected allogeneic pancreatic cell lines Panc 10.05 and Panc 6.03 as a participant in either one of the Hopkins IRB protocols: application number 96-01-25-01 entitled “A Phase I Clinical Trial of Lethally Irradiated Allogeneic Pancreatic Tumor Cells Transfected with the GM-CSF Gene for the Treatment of Adenocarcinoma of the Pancreas”, SKCCC J9617, or application number 00-01-13-02, entitled “A Safety and Efficacy Trial of Lethally Irradiated Allogeneic Pancreatic Tumor Cells Transfected with the GM-CSF Gene in Combination with Adjuvant Chemoradiotherapy for the Treatment of Adenocarcinoma of the Pancreas”, SKCCC J9988, at least 6 months ago;

OR

Completed surgery and any adjuvant therapy at least 28 days prior. Treatment administered in conjunction with surgery is at the discretion of the local oncologists. Options may include: neo-adjuvant chemotherapy, neo-adjuvant radiation, post-surgical adjuvant chemotherapy, post-surgical adjuvant radiation.

3. Received the last anti-cancer therapy at least 28 days ago.
4. Provide informed consent.
5. Have an Eastern Cooperative Oncology Group (ECOG) performance status of 0 or 1.
6. Have adequate hematologic function (Hemoglobin \geq 9 gm/dl, ANC \geq 1500#/cu mm, platelets \geq 100,000 K/cu mm)
7. Have adequate renal function (Serum creatinine \leq 2 mg/dL).
8. Have adequate hepatic function (Bilirubin \leq 2.0 mg/dL, unless known Gilbert's Syndrome; AST, ALT and amylase \leq 2x upper limit of normal; Alk Phos \leq 5x upper limit of normal.)
9. Agree to use adequate birth control, if of childbearing potential.

3.2.3 Exclusion Criteria for First Vaccination:

Research participants with any of the following will be excluded from study entry:

1. Radiographical evidence of pancreatic cancer disease recurrence.
2. Documented history of autoimmune diseases including systemic lupus erythematosus, sarcoidosis, rheumatoid arthritis, glomerulonephritis, or vasculitis.
3. Uncontrolled medical problems.
4. Systemic steroid therapy within 28 days before vaccine administration.
5. Anticipated need for systemic steroid therapy within 28 days after vaccine administration.
6. Evidence of active infections.
7. Pregnant.
8. History of another cancer (other than pancreatic cancer) in the past five years except for treated non-melanoma skin cancer, superficial bladder cancer, or carcinoma-in-situ of the cervix.

3.2.4 Inclusion Criteria for Boost Vaccination:

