4.0 Statistical Considerations

4.1 Sample Size

The primary statistical endpoint of this study is to evaluate the safety and feasibility of vaccine boosting with lethally irradiated allogeneic pancreatic tumor cells transfected with the GM-CSF gene. Among patients who have previously been treated with the vaccine, the cohort is limited to those who continue to have no disease recurrence for at least 1 year after treatment. Currently, there are three potentially eligible patients from the original phase I study, and 14 from the phase II study. A total of up to 17 previously treated patients will be eligible to continue to receive vaccine treatment in the form of semi-annual boosts. The second cohort of vaccine naïve patients who have been recurrence free for at least 28 days following adjuvant therapy will be given three priming vaccines each a month apart, followed by semi-annual vaccine boosts in order to determine the feasibility of administering the vaccination to vaccine naïve patients and to obtain initial estimates of the efficacy of such treatment with respect to prolonging disease-free status. As of Amendment #9, participants will be switched to annual vaccinations. We will base our determination of feasibility by estimating the proportion of patients with a dose limiting toxicity (DLT) within 28 days of the first vaccine treatment. Between 20 and 45 vaccine naïve patients will be included. An initial group of 20 patients will be recruited and an interim analysis will be performed in order to guard against excessive toxicities relating to treatment. No DLTs have been observed in either the phase I or II studies. If there is significant evidence that more than 10% of the vaccine naïve patients have dose limiting toxicities within 28 days of the first vaccination, then the trial will be halted. If 6 out of 20 of the initial patients have DLTs, the lower bound of the exact 95% confidence interval for the proportion of patients with a DLT is 11.89%. Therefore, we will halt the trial due to excessive toxicity at the interim analysis if 6 or more patients have a DLT within the first 28 days of their first vaccine. Otherwise, an additional 20 vaccine naïve patients will be accrued. If 20 patients are accrued, the maximum width of the 95% confidence interval estimate of the proportion of patients with a DLT is 0.438. If the full cohort of 40 patients is accrued, then the maximum width of the 95% confidence interval is 0.309.

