4.3.1 Efficacy endpoints

The primary efficacy endpoint of interest is the overall survival (OS) of patients treated with vaccine boosts. The overall survival is defined as the time from the first vaccine boost until death. If a patient is lost to follow-up or the study is ended prior to death, the patient will be considered censored at their last recorded follow-up. For each cohort, Kaplan Meier curves will be constructed and the median survival estimates will be calculated with 95% confidence intervals using Greenwood's formula. Since the time between completion of treatment and the initiation of vaccine boosts will vary among subjects, we will use a Cox proportional hazards model to adjust for this delay in boosts.

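### The historical controls in section 5.1 have no recurrence-free requirement and no time zero, so the survival comparison is likely to favour the vaccine even if it has no effect

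*Combined protocol and SAP*

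**What the plan says.** Section 5.1 (Evaluation of Clinical Activity) says patients are monitored for disease-free and overall survival, and then: "The results from this trial will be compared to historical controls seen at the Johns Hopkins Hospital (5". It describes the most accurate controls as recent patients of the same hospital "who can be matched for pathologic stage, surgical intervention, and adjuvant combination chemotherapy and radiation therapy". No other matching factor is named, and no starting time is given for the controls.

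The conditions on trial patients are spread over other sections:

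- Sections 3.2.3 and 3.2.5 list the same exclusion for the first vaccination and for every boost: "Radiographical evidence of pancreatic cancer disease recurrence".
- For vaccine-naive patients, section 3.2.2 requires "Completed surgery and any adjuvant therapy at least 28 days prior", with no upper limit. Section 4.1 describes them as "vaccine naïve patients who have been recurrence free for at least 28 days following adjuvant therapy".
- For previously vaccinated patients, section 4.1 says "the cohort is limited to those who continue to have no disease recurrence for at least 1 year after treatment".
- Section 4.3.1 sets the main efficacy clock: "The overall survival is defined as the time from the first vaccine boost until death". Recurrence-free survival (called PFS there) runs from the first vaccine.
- Section 3.4.1 places the first boost of naive patients six months after the third monthly priming vaccine.

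Section 4.3.1 also has a Cox model for the varying delay before boosting. Section 4.3 calls the secondary analyses primarily descriptive.

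**The concern.** Recurrence is the main route to death in this disease. A trial patient contributes OS time only after passing a scan without recurrence at the first vaccine and another at the first boost. A naive patient who recurs or dies between the two never reaches the OS time zero. A control who recurs or dies over the same period is still counted, because nothing in section 5.1 removes that control. Matching on stage, surgery and adjuvant treatment cannot correct this, since none of the three records whether the patient was still recurrence free months later. The Cox model in section 4.3.1 works among trial patients only and does not align the controls.

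This is the only external survival comparison the plan describes, and section 4.3 intends the efficacy results to shape hypotheses for later trials. A gap produced by selection could be read there as a signal of benefit.

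**Working it through.** The plan gives no test, effect size or control number for this comparison, so it has no figure to reproduce. The check below asks what 24-month OS would be in each group if the vaccine did nothing.

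**Inputs from the documents**
- Median OS after resection: 18 months (section 2.6).
- Long-term survivors: 1 − 0.79 = 0.21, because section 2.1 says 79% eventually die of recurrence after surgery and adjuvant therapy.
- Adjuvant treatment in the earlier phase I trial: 6 months (section 2.7.1).

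**Assumptions**
- Median recurrence-free time m of 9 or 12 months from surgery. Section 2.6 says only that many have recurred one year after surgery.
- First boost in naive patients: 2 months to the start of adjuvant therapy + 6 months of therapy + 1 month wait + 56 days (about 1.8 months) of priming + 6 months = about 17 months after surgery.
- Controls timed from surgery.
- Long-term survivors (fraction c) neither recur nor die in the period studied. Everyone else recurs at a constant rate a and then dies at a constant rate b.

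**Formulas**
- a = ln[(1 − c)/(0.5 − c)]/m
- U(t) = [b·exp(−at) − a·exp(−bt)]/(b − a) is survival t months on for a recurrence-free patient who is not a long-term survivor.
- Controls: S(t) = c + (1 − c)·U(t), with b chosen so that S(18) = 0.50.
- Recurrence free at 17 months: R = c + (1 − c)·exp(−17a). Share of long-term survivors among them: q = c/R.
- Trial patients, t months after the boost: T(t) = q + (1 − q)·U(t).

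**With 21% long-term survivors**
- m = 9: a = 0.1114, b = 0.1285, U(24) = 0.220. Controls: 0.21 + 0.79 × 0.220 = 0.384. R = 0.329 and q = 0.638. Trial: 0.638 + 0.362 × 0.220 = 0.718.
- m = 12: a = 0.0835, b = 0.1945, U(24) = 0.229. Controls: 0.21 + 0.79 × 0.229 = 0.391. R = 0.401 and q = 0.524. Trial: 0.524 + 0.476 × 0.229 = 0.633.

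**With one constant recurrence hazard (c = 0)**
Here q = 0, so T(t) and S(t) are the same function. Both groups have 24-month OS of 0.347 (m = 9) or 0.360 (m = 12).

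**Controls required only to be alive at 17 months, both clocks started there**
Control survival becomes S(41)/S(17).

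| Scenario, 24-month OS | Trial | Controls from surgery | Controls alive at month 17 |
|---|---|---|---|
| c = 0.21, m = 9 | 72% | 38% | 0.245/0.524 = 47% |
| c = 0.21, m = 12 | 63% | 39% | 0.255/0.523 = 49% |
| c = 0, m = 9 | 35% | 35% | 0.110/0.529 = 21% |
| c = 0, m = 12 | 36% | 36% | 0.137/0.527 = 26% |

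Requiring controls only to be alive leaves a gap in every row, and creates one where there was none.

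**Sensitivity to the time of the boost.** With c = 0.21 and controls from surgery (38-39%), the trial figure is 51-55% for a time zero at 9 months, 55-61% at 12 months and 65-74% at 18 months.

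**Controls recurrence free at the same landmark, both clocks started there.** The two survival formulas are then identical. Simulation of 45 trial patients against 90 controls with 36 months of follow-up (the control number and follow-up are assumed) gives null hazard ratios of 0.99 to 1.02.

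**The case against.** The strongest reply is that the bias is not certain. Section 4.3.1 starts OS at the first boost, and on that clock, with controls timed from surgery, a homogeneous constant hazard gives no difference at all. This stands. A reader might infer that the vaccine is bound to look effective, but the documents do not support that. They do make heterogeneity the more plausible case: 21% do not die of recurrence, and sections 2.7.1 and 2.7.3 report long-term disease-free survivors.

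A reader might also time both groups from surgery, which gives a much larger gap. No section plans to time trial survival from surgery, so that figure does not describe this plan.

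A third tempting reading is that 17 eligible out of 74 earlier recipients (14 in phase I, 60 in phase II), or 23%, measures the selection. It does not. Only 36 phase II patients were evaluable at two years (section 2.8.1), so some may have lacked follow-up rather than recurred.

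The preferred controls must have survived long enough to receive adjuvant therapy, so timing them all from surgery with an 18-month median is approximate. This may narrow the gap. It does not show that they were recurrence free afterwards. The control series itself cannot be identified, because reference 5 points to an unnumbered list.

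Finally, efficacy is secondary and descriptive, and no formal test against controls is specified. That limits the consequence but does not remove the tilt in a descriptive comparison.

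**Conclusion.** The point holds as a likely bias in favour of the vaccine, of uncertain size. With time zero at a boost about 17 months after surgery, controls timed from surgery, median OS of 18 months, 21% long-term survivors and a median recurrence-free time of 9-12 months, a vaccine with no effect would show 24-month OS of about 63-72% against 38-39%. Under one constant hazard for all patients the difference on that clock is nil.

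The documents fix neither the controls' time origin nor the time from surgery to boost, so these figures are illustrations and not predictions. They cover OS in the naive cohort. The same mechanism applies to recurrence-free survival and to the previously vaccinated cohort, but neither was sized.

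Severity is should-fix. A reader might infer that the flaw undermines the trial. It does not: the primary endpoint is safety, the stopping rule in section 4.1 rests on dose-limiting toxicity, and the single-arm Kaplan-Meier estimates need no controls.

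**What to change.** In section 5.1, add to the matching rule that a control qualifies only if alive, radiographically recurrence free and off anti-cancer therapy for at least 28 days at the same time since surgery as the matched trial patient's time zero. Start both clocks at that point.

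Take the time zero from the endpoint being compared, so that section 5.1 agrees with section 4.3.1: the first boost for OS and the first vaccine for recurrence-free survival. Do this separately for the two cohorts. Identify the control series, since the present citation does not.

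Where such controls cannot be found, make no historical comparison and report only the single-arm Kaplan-Meier estimates.

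The cost is a change of wording and a review of hospital records for control recurrence and treatment dates. There will be fewer eligible controls, and the comparison will probably look less favourable.
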